8.7.3 Overview of the Research Biosample Repository

The Roche RBR is a centrally administered group of facilities for the long-term storage of human biologic samples, including body fluids, solid tissues, and derivatives thereof (e.g., DNA, RNA, proteins, peptides). The collection, storage, and analysis of the RBR samples will facilitate the rational design of new pharmaceutical agents and the development of diagnostic tests, which may allow for individualized drug therapy for patients in the future.

Samples for the RBR will be collected from participants who give specific consent to participate in this optional RBR. Collected RBR samples will be used to achieve the following objectives:

- To study the association of biomarkers with efficacy, AEs, or progressive disease.
- To identify safety biomarkers that are associated with susceptibility to developing AEs or can lead to improved AE monitoring or investigation.
- To increase knowledge and understanding of disease biology and drug safety.
- To study treatment response, including drug effects and the processes of drug absorption and disposition.
- To develop biomarker or diagnostic assays and establish the performance characteristics of these assays.

8.8 BIOMARKER SAMPLES

8.8.1 Mandatory Samples

The following samples are required and will be collected from all participants in this study:

- Whole blood sample for DNA extraction (see Section 8.7.2)
- Hair samples for exposome analysis (see Section 8.7.1.2)
 - Note: No hair samples will be collected from study participants with no or insufficient hair.

A mandatory whole blood sample will be taken for DNA extraction to support clinical genotyping from every participant at any convenient time between Day 1 and follow-up

visit. In addition, hair samples for exposome analysis will be collected at the timepoints specified in the SoA (see Section 1.3).

Clinical genotyping samples and derived analytical material will be destroyed within 5 years following completion of the CSR. Hair samples for exposome analysis will be destroyed within 2 years following completion of the CSR. For sampling procedures, storage conditions, and shipment instructions, see the separate laboratory manual and instructions.

For participants who consent to RBR, leftover blood and hair samples will be transferred to RBR (see Section 8.9).

8.8.2 Optional Samples

Optional hair samples will be collected from support persons who provide consent on the applicable ICF at the timepoints specified in the SoA (see Section 1.3). These optional samples will serve as a control to assess the potential contribution of shared environmental factors in the exposome analysis (see Section 8.8.1).

8.9 SAMPLES FOR RESEARCH BIOSAMPLE REPOSITORY

8.9.1 Sample Collection

The following samples will be stored in the RBR and used for research purposes, including, but not limited to, research on biomarkers related to ASD and related disorders and drug safety:

- Leftover PK samples (see Section 8.5)
- Leftover genetic sample (see Section 8.8.1)
- Additional whole blood sample for RBR on Day 1 predose and at Week 12 or Early Termination visit (see SoA in Section 1.3)
- Leftover hair samples of the study participants (see Section 8.8.1)

The sample collected for DNA extraction include, but is not limited to, genomic analysis and may be sent to one or more laboratories for analysis of germline or somatic mutations via whole genome sequencing (WGS), whole exome sequencing (WES), next-generation sequencing (NGS), or other genomic analysis methods.

Genomics is increasingly informing researchers' understanding of disease pathobiology. WGS provides a comprehensive characterization of the genome and, along with clinical data collected in this study, may increase the opportunity for developing new therapeutic approaches. Data will be analyzed in the context of this study but will also be explored in aggregate with data from other studies. The availability of a larger dataset will assist in identification of important pathways, guiding the development of new targeted agents.

The hair samples may likewise be sent to other laboratories and analyzed with exposomic methods. Biochemical assays of the hair samples will allow molecular phenotyping, which is not possible with blood analysis alone. These data will interface with other datasets, including genomics data, to support the identification of potential new targets and pathways.

Participants will not be identified by name or any other personally identifying information. Data generated from RBR samples will be analyzed in the context of this study but will also be explored in aggregate with data from other studies. The availability of a larger dataset will assist in identification and characterization of important biomarkers and pathways to support future drug development.

For all samples, dates of consent and sample collection should be recorded on the associated RBR page of the eCRF. Details on processes for collection and shipment of these samples can be found in separate sample documentation.

RBR samples will be stored and used until no longer needed. The RBR storage period will be in accordance with the IRB/EC-approved ICF and applicable laws (e.g., Health Authority requirements).

The repository samples will be subject to the confidentiality standards (as described under Confidentiality and in Appendix 1).

8.10 HEALTH ECONOMICS OR MEDICAL RESOURCE UTILIZATION AND HEALTH ECONOMICS

Health Economics/Medical Resource Utilization and Health Economics parameters are not evaluated in this study.

8.11 TIMING OF STUDY ASSESSMENTS

8.11.1 Screening and Pre-treatment Assessments

Written informed consent for participation in the study must be obtained before performing any study-specific screening tests or evaluations. Informed Consent Forms (ICFs) for enrolled participant and for participants who are not subsequently enrolled will be maintained at the study site.

All screening assessments (related to entry criteria), must be completed and reviewed to confirm that participants meet all eligibility criteria. The Investigator will maintain a screening log to record details of all participants screened and to confirm eligibility or record reasons for screening failure.

Screening and pretreatment assessments (i.e., assessments at the pre-baseline and baseline visits) will be performed at the timepoints indicated in the SoA (see Section 1.3); however, in case of unexpected delays due to logistical or technical reasons (e.g., sickness of support persons or raters), the screening or pre-treatment period (see Figure 1) may be extended to up to 2 additional weeks. Beyond these 2 weeks, the participant is considered a screen failure, but can be re-screened (see Section 5.4).

Once all inclusion and exclusion criteria are met, the EAF (see Sections 1.3 and 8.2.1) is sent to the external vendor as part of the screening process, ideally before the pre-baseline visit. The Principal Investigator will decide whether a participant will be enrolled and may consult with the Sponsor (Medical Monitor or designee) for advice or clarification of any eligibility criteria.

The Principal Investigators are highly encouraged to use the voluntary eligibility consultation offered by the external vendor to ensure meeting all eligibility criteria and avoid protocol deviations related to participant eligibility.

For a participant to enter the randomized, double-blind treatment period the following criteria must be fulfilled:

- No significant new or worsening psychiatric or medical illness since screening that in the opinion of the Investigator would interfere with the participant's ability to participate in the study.
- No change in medications since screening.

8.11.2 Assessments during Treatment

Under no circumstances will participants who enroll in this study and have completed treatment as specified be permitted to be allocated a new randomization number and reenroll in the study.

All assessments must be performed as per SoA (see Section 1.3). The recommended order of assessments to be performed at the clinic will be defined in a separate document. The order of assessments may be adapted to allow efficient administration of all assessments at the site with the exception of assessments that have to be done at a specific time before or after taking the study drug as per SoA (see Section 1.3). The order of assessments that have to be taken at home is predefined on the electronic device for each participant (see Section 8.7.1.1). The site will contact the participant or support person over the phone to assess for any clinically significant symptoms and/or new medication, to ensure compliance to the study drug and digital biomarker assessments as well as to administer questionnaires/scales/tests when appropriate as per SoA (see Section 1.3).

8.11.3 Assessments at Follow Up /Early Termination Visit

Participants who complete the 12-week study treatment period will be asked to return to the clinic approximately 2 weeks and 6 weeks after the last dose of study treatment for safety follow-up visits (see Section 1.3).

Assessments at the follow-up/early termination visits will be performed as indicated in the SoA (see Section 1.3). After the study completion/early termination visit, AEs should be followed as outlined in Sections 8.3.1 and 8.3.3.

If participants discontinue from the study early (as described in Section 4.1.2 and Section 7), all efforts should be made to ask participants to return to the clinic for an early termination visit. All AEs should be followed up until they are resolved and additional unscheduled safety assessments should be performed at Investigator's discretion after discussion with the Medical Monitor if required.

8.11.4 **Assessments at Unscheduled Visits**

Unscheduled visits will be performed for safety reasons (e.g., for repetition of safety laboratory sampling). If due to a safety-related event a participant is unable to physically go to the site for an unscheduled visit, blood and urine samples may be collected by the home nurse services.

The unscheduled visit should be used to collect all assessments that are missing at that time.

If a COA (see Section 8.1.5) cannot be completed during the visit or for a scale, the total score (e.g., the composite scores for Vineland™-3) cannot be calculated with the available data, the scale should be repeated via the phone within the corresponding visit window or at an unscheduled visit as soon as possible (within the next 7 days).

9. STATISTICAL CONSIDERATIONS

9.1 STATISTICAL HYPOTHESES

Because the nature of this Phase II study is purely hypothesis generating, no formal testing of a predefined null hypothesis is performed.

9.2 SAMPLE SIZE DETERMINATION

Approximately 105 participants with ASD randomized in a 1:1:1 ratio between two active dosing regimens and placebo need to be recruited in order to obtain evaluable data from approximately 84 participants after 12 weeks of treatment. Evaluable data from 84 ASD participants provides at least 80% power to detect a mean difference between baseline and 12-week follow-up of 4.5 points on a Vineland™-3 composite between any active treatment arm and the placebo arm with α = 0.10 error control (1-sided). The minimally

detectable difference in this cohort is 2.7 points. It is assumed that the standard deviation of the differences between baseline and 12 weeks follow up is 8.0 points, that 20% of participants will not provide evaluable data, and that the participants recruited will consist of at most 25% low-functioning participants, at most 25% female participants, and at most 75% adults. Because the purpose of this study is exploratory, no adjustment for comparison of multiple active doses to a single placebo arm is performed.

9.3 POPULATIONS FOR ANALYSES

For purposes of analysis, the following populations are defined in Table 11.

Table 11 Analysis Populations

Population	Description
Safety	All participants randomized to study treatment and who received at least one dose of the study treatment, whether prematurely withdrawn from the study or not, will be included in the safety analysis.
Pharmacokinetic	All participants providing pharmacokinetic data will be included in the PK Population. Participants will be excluded from the PK analysis population if they significantly violate the inclusion or exclusion criteria, deviate significantly from the protocol, or if data are unavailable or incomplete which may influence the PK analysis. Excluded cases will be documented together with the reason for exclusion. All decisions on exclusions from the analysis will be made prior to database closure.
Efficacy	All participants who give informed consent, are randomized, and receive at least one dose of double-blind study medication. Data will be analyzed as per the actual treatment received.

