4.1.1 Length of the Study

The total duration of the study for each participant will be up to 24 weeks (approximately 5.6 months), divided as follows:

- Screening period of at least 2 weeks and up to 4 weeks
- Study pre-baseline and baseline period (2 weeks)
- Study treatment period with fixed dose (12 weeks)
- Safety and efficacy follow-up period (6 weeks).

4.1.2 Individual Stopping Criteria

Dosing will be stopped at any time during the study in a given individual participant if one of the following circumstances occurs, unless it is determined by the Investigator that the occurrence is not related to the administration of the study drug:

- QTc: A confirmed QTcF (average of triplicate values) above 480 ms or a change from baseline by more than 60 ms (when confirmed in repeat measurement within 30 minutes), will result in drug interruption. For the assessment of the QTcF stopping rule, central ECG readings should be used to determine whether the criteria have been met. An expedited review by the central vendor should be requested by the Investigator to ensure that the results are available before the next administration of the study drug. If the central readings are not available at the time of next dosing, this stopping criterion will apply. Study drug may be resumed with the joint agreement of the Investigator and the Sponsor's Medical Monitor when follow-up test results show that the participant no longer meets the dose interruption criteria.
- **Liver safety:** Any participant with the occurrence of either of the following liver values will be discontinued:
 - ALT or AST >3 x ULN and bilirubin >2 x ULN
 - ALT or AST >3 x ULN associated with symptoms (new or worsening) believed to be related to liver injury or hypersensitivity
- Other findings which, at the joint discretion of the Sponsor's Medical Monitor, the Sponsor Safety Science Leader and the Investigator, indicate that dosing in this individual should be stopped (e.g., severe sedation/somnolence, cognitive impairment) (see also Table 10).

Ultimately and in case of disagreement, the Investigator remains responsible for the decision to stop dosing.

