4.1.3 Administrative Structure

4.1.3.1 Internal Monitoring Committee (IMC) and Scientific Oversight Committee (SOC)

An IMC consisting of a selected subset of Roche representative(s) as identified in the "IMC Agreement" will be responsible to perform interim analyses of accumulated safety, tolerability, PK, and efficacy (as required) data. The IMC members, the clinical

pharmacologist, and the pharmacometrician will be unblinded to individual study treatment allocation (see Section 6.3 for treatment allocation and blinding of data).

An SOC consisting of at least one external expert will support the IMC in making their recommendations. These SOC members will likewise be unblinded to individual study treatment allocation.

Access to treatment assignment information will follow the Sponsor's standard procedures (see Section 6.3).

On the basis of accumulated study data available at their review, the IMC and SOC may recommend adjustment(s) of the dose levels, dosing regimen, or the timing of dosing (see Section 6.6).

Further details can be found in the "IMC Agreement" and in Section 9.5 (Interim Analyses).

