6.6 DOSE MODIFICATION

Participants will be randomized to receive either

Dependent on the safety observations, the timing of dosing or the dose level may be adjusted during the treatment period (see Section 4.1.3 and Section 8.3.7.2). In addition, a different dosing regimen may be explored if warranted on the basis of the safety profile of RO7017773 (e.g., exploration of dose titration or tapering). This would be done on the basis of IMC and SOC recommendation and after discussion with the Sponsor's Medical Monitor.

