1. INTRODUCTION

The objectives of this Phase 2 proof-of-concept study (BP41316) is to investigate the efficacy, safety, and tolerability of Alogabat in adolescents and adults (15 to 45 years of age) with autism spectrum disorder (ASD), with a target on the core symptoms of ASD of social communication deficits, and restricted and repetitive behaviors (RRBs) and interests. In addition, a set of biomarkers linked to the mechanism of action of the study drug or to ASD-related alterations is investigated in a representative patient population to pilot the identification of responder subgroups. To date, very few studies have investigated the effect of pharmacological treatments on the core symptoms of ASD and consequently no pharmacological agents are approved that offer a treatment for the core symptoms in this population of high unmet clinical need.

A key challenge in the development of new therapies to treat the core symptoms in ASD is the change of symptoms across different stages of development in longitudinal studies in both social communication deficits as well as in RRBs (Simonoff et al. 2020; Richler et al. 2010; Pender et al. 2020). The presentation of RRBs is known to be associated with age and the level of intellectual functioning (Lam and Aman 2007, Esbensen et al 2009, Richler et al 2010, Kim and Lord 2010, Uljarevic et al 2022). Thus, interventions may have different effects, depending on age and intelligence quotient (IQ), on individuals with ASD and treatment effects in older adolescents and adults may not be extrapolated to effects in the pediatric population, given the potential difference in manifestations, both quantitatively and qualitatively, of social communication deficits and RRBs with age.

Adolescents and adults aged 15 to 45 years with ASD are enrolled in this study to allow for the generation of data on the safety and tolerability, and the potential efficacy in these age groups.

Analyses of the primary and secondary endpoints as described in the protocol will be performed as planned.

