3. ANALYSIS SETS

The analysis data sets for the purposes of analyses are presented in Table 3.

Efficacy analyses based on the Efficacy Analysis Population will be restricted in a way that assessments at week 12 will be excluded from the efficacy analyses if the participant missed more than 7 consecutive study medications immediately preceding the day of the assessment (if performed), or if the overall IMP compliance, i.e. the ratio of administered study medication to planned study medication until the assessment, was < 60%.

Post treatment EEG assessments will be excluded from the PD analysis if the last dose of study medication was taken more than 6 hours before the EEG. Additionally, Week 2 and Week 12 EEG assessments will be excluded from the PD analysis if the study participant missed more than 3 doses in the week preceding the EEG.

Table 3 Analysis Sets

Population	Description
Safety Population	All participants randomized to study treatment and who received at least one dose of the study treatment, whether prematurely withdrawn from the study or not, will be included in the safety analysis.

Pharmacokinetic Population	All participants providing pharmacokinetic data will be included in the PK Population. Participants will be excluded from the PK analysis population if they significantly violate the inclusion or exclusion criteria, deviate significantly from the protocol, or if data are unavailable or incomplete which may influence the PK analysis. Excluded cases will be documented together with the reason for exclusion.
Efficacy Analysis Population	All participants who give informed consent, are randomized, and receive at least one dose of double-blind study medication.

4. STATISTICAL ANALYSES

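### The protocol assigns efficacy data by treatment actually received, the SAP states no assignment rule, and neither defines actual treatment after a dispensing error or dose change

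*Protocol*

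**What the plan says.** **Protocol, Section 9.3, Table 11.** The Efficacy row takes everyone who consented, was randomised and had at least one dose, and adds: "Data will be analyzed as per the actual treatment received". The Safety row has no rule for assigning participants to arms. Section 9.4.2 uses the efficacy population for the primary and secondary analyses.

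**SAP, Section 3, Table 3.** The efficacy population is "All participants who give informed consent, are randomized, and receive at least one dose of double-blind study medication". The as-treated sentence is absent and nothing replaces it. The ANCOVA in Section 4.2.2 has treatment levels placebo, low dose and high dose, without saying whether these are assigned or received. Section 1 says: "Analyses of the primary and secondary endpoints as described in the protocol will be performed as planned".

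**Dose changes.** Protocol Section 4.1.1 describes a fixed-dose treatment period. Section 6.6 says that, depending on safety observations, "the timing of dosing or the dose level may be adjusted during the treatment period". After a further sentence on other regimens it adds: "This would be done on the basis of IMC and SOC recommendation and after discussion with the Sponsor's Medical Monitor". Under Section 4.1.3.1, "the IMC and SOC may recommend adjustment(s) of the dose levels, dosing regimen, or the timing of dosing".

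**Use of the result.** SAP Section 2.1 plans no formal hypothesis test but bases gating criteria on the ANCOVA p-values.

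**The concern.** The usual convention is efficacy as randomised and safety as treated. Table 11 puts the as-treated rule under efficacy and none under safety.

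The two contrasts with placebo are randomised comparisons only while arm membership is fixed at randomisation. If a participant is reassigned because of something that happened on treatment, and that reason is related to outcome, one active arm loses its poorer responders and the other gains them. Both contrasts and the dose-response reading are then affected.

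The rule also cannot be applied without a definition. Study drug is dispensed on Day 1 and at Week 6 (protocol Table 1), so an error at one of these visits leaves a participant with mixed treatment. A change of dose level does the same. Neither document says whether the first, the predominant or the last treatment decides the arm.

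**Working it through.** **Inputs from protocol Section 9.2 and SAP Section 2.2:** 84 evaluable participants (28 per arm), SD of change 8.0, target difference 4.5, one-sided alpha 0.10, minimally detectable difference 2.7, 20% not evaluable.

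**The plan's own figures**
- Standard error of a contrast: 8 × √(2/28) = 2.14.
- Minimally detectable difference: 1.2816 × 2.14 = 2.74, against 2.7 stated.
- Power: Φ(4.5/2.14 − 1.2816) = 0.795, against at least 80% stated.
- Randomised number: 84/0.80 = 105, as stated.

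These figures are not in dispute, and the choice of assignment rule does not change them.

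**Illustration. Both m and D are assumptions, since the documents give no rate of dose changes or dispensing errors.** Suppose the drug has no effect and each arm of 28 contains m participants whose change is D points worse than the rest. As randomised, every arm mean is lower by mD/28, so both contrasts are zero. Now count the m high-dose participants in the low-dose arm:
- bias of the high-dose contrast = 0 − (−mD/28) = +mD/28;
- bias of the low-dose contrast = −2mD/(28 + m) + mD/28;
- one-sided error for the high-dose contrast = Φ(bias/SE − 1.2816), with SE = 8 × √(1/28 + 1/(28 − m)).

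| m | D | High-dose bias | Low-dose bias | One-sided error, high dose |
|---|---|---|---|---|
| any of 1, 2, 3, 5 | 0 | 0 | 0 | 0.100 |
| 1 | 4 | +0.14 | −0.13 | 0.112 |
| 3 | 4 | +0.43 | −0.35 | 0.139 |
| 5 | 4 | +0.71 | −0.50 | 0.167 |
| 3 | 8 | +0.86 | −0.69 | 0.186 |
| 5 | 8 | +1.43 | −1.00 | 0.259 |

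For m = 3 and D = 4 (half the assumed SD), the shift is 3 × 4/28 = 0.43. That is 0.43/2.14 = 0.2 of the standard error, 0.43/2.7 = 16% of the minimally detectable difference, and 0.43/4.5 = just under 10% of the target.

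If only the high-dose arm contains such participants, the as-randomised high-dose mean is 0.43 lower. As treated, that deficit disappears and the low-dose mean falls by 3 × 4/31 = 0.39. The high-minus-low difference goes from −0.43 to +0.39.

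**The price of analysing as randomised.** If 3 of 28 high-dose participants in fact received placebo, 4.5 points is diluted to 4.5 × 25/28 = 4.02 and power falls to 72%. The type I error does not rise.

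**The case against.** The strongest reply is that the route from a dose change to a change of arm is not in the documents.

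- **Reassignment after a dose change.** A reader might infer that dose adjustments do move participants between arms. No passage says so. If actual treatment means the arm's supply given on Day 1, a later adjustment moves nobody. The dose levels are redacted, so it cannot be seen whether an adjusted high dose would equal the low dose.
- **Individual dose reduction.** Section 4.1.3.1 has the committees recommend dose-level changes from accumulated data, and a change made to a whole arm moves no individual across. In Section 6.6 it is unclear whether the closing condition covers the dose-level sentence. The event guidance in Section 8.3.7.2 names changing the time of dosing, pausing, restarting or stopping, but no reduction of dose level.
- **The rule in the final analysis.** A reader might infer from SAP Section 1 that the as-treated rule carries over. The same SAP drops both interaction terms from the main model and moves from 90% to 80% confidence intervals, so that sentence cannot import every protocol detail. The SAP's rule is better called unspecified.
- **Occurrence.** SAP Section 1.2 reports adequate safety and tolerability at both interim reviews. Section 1.2.3 mentions dose adjustment only as something that could have been recommended. Packs are assigned centrally. Dispensing errors may also be unrelated to outcome, in which case D is near zero and so is the bias.

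All of this limits the size and likelihood of the problem. None of it supplies an assignment rule. The protocol's sentence is still the only one written down, and a participant given another arm's treatment throughout would be counted outside the randomised arm under it, whatever the dose-change provisions mean.

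**Conclusion.** The point holds as a gap in specification. The protocol sets an as-treated rule for efficacy, the SAP neither keeps nor replaces it, and neither document defines actual treatment where a participant's treatment is mixed. That leaves arm membership open for the contrasts behind the gating criteria.

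The documents do not support saying that bias has occurred or is likely to be large. With no errors or dose changes, or with movers whose outcomes match the rest, the effect is nil. The 0.43-point shift rests on 28 evaluable per arm, 3 participants moved and a 4-point deficit, and the last two are assumed. Nor are the fixed-dose description and Section 6.6 necessarily contradictory: one may state the planned regimen and the other a contingency. They should still be reconciled. The trial is exploratory, but the change is worth making because it costs almost nothing and removes a choice that could otherwise be made after unblinding.

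**What to change.** 1. In protocol Table 11, delete the as-treated sentence from the Efficacy row. In that row, and by addition in SAP Table 3 and Section 4.2.2, state that the treatment factor in the ANCOVA is the arm assigned at randomisation, regardless of what was dispensed or of any later change in dose level.
2. Put the as-treated rule in the Safety row of both tables, with a definition of actual treatment for participants who received more than one treatment or dose level.
3. Optionally keep an as-treated efficacy analysis as a sensitivity analysis, using the same definition.
4. Have the sponsor reconcile the fixed-dose description in Section 4.1.1 with the dose-adjustment provision in Section 6.6.

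The cost is a few sentences. No new data are needed and the sample size stays at 84 evaluable and 105 randomised. Listings of protocol deviations and drug administration are already planned (protocol Section 9.6, SAP Appendix 1), so little new output is required.

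This does not touch the separate exclusions in SAP Section 3, which remove Week 12 assessments after more than 7 consecutive missed doses or with compliance below 60%. Those would still depart from a full as-randomised comparison.
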